**11.2 Sample Size:**

900 active duty service members

**11.3 Total number of subjects requested (including records and specimens):**

900

**11.4 If you are recruiting by study arm, please identify the arms of the study and how many subjects will be enrolled in each arm**

**11.5 Please provide a justification for your sample size**

Power analysis indicates that a sample of 720 will be sufficient to have 80% power to detect small main effects and interaction effects at a 5% significance level. Accounting for 20% attrition, up to 900 service members will be enrolled to reach target sample size.

Of this total sample, it is anticipated that 40 participants will be needed and selected to complete an interview. Qualitative data analysis does not lend itself to power analysis. Sample size was selected based on the experiences of our qualitative experts.

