Participants will be randomized to one of the 32 treatment conditions, corresponding to all factorial combinations of randomized components. The randomization scheme will be generated based on a permuted block randomization procedure, with small random sized blocks. Randomization will be stratified by sex. The length of the intervention will vary based on which components (which treatment condition) the participant receives. The components include: (1) a basic sexual and reproductive health (SRH) education (not randomized), (2) video narratives, (3) skills building videos, (4) interactive scenarios, (5) a future life planning tool, and (6) epidemiological risk scenario.

The basic SRH education component is the only component that every participant will receive; all other components will have two levels (i.e., "on" or "off"). The exact educational content the participant receives in this component will be determined based on baseline SRH knowledge, which will be assessed in a pre-test (discussed below). In the basic SRH education component in

the app, participants will be presented with a series of screens with interactive content and occasional videos.

The narrative video component contains videos about situations related to SRH. This component is randomized and is either "on" or "off" (i.e., received or not received by a participant). Narrative videos will include stories of individuals engaging in positive and negative sexual health behaviors that leads to either positive and negative outcomes, respectively. Those who receive the narrative video component in the app will be expected to watch the assigned videos.

The skills building video component contains videos on how to perform or engage positive SRH behaviors, such as correctly using a condom and what to expect when having a Pap smear. This component is randomized and is either "on" or "off". Participants who receive this video component in the app will be expected to watch the assigned videos.

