that corresponds with the assigned treatment condition and that is tailored based on her or his completion of the SRH Knowledge Pre-Test Assessment. All interaction with the app will be identified only by the access code and PIN combination. It is anticipated that the app will take up to one hour to complete, depending on how many and what components a participant receives.

A USU-based research team member will then contact the participant via email to ask her or him to complete the Participant Post-Intervention Assessment (attached; identified by RIN only) in an online data collection software (e.g., REDCap, SurveyMonkey) around two weeks after the participant was asked to complete the app. All questions in the Participant Post-Intervention Assessment must be answered. However, a participant may respond that she or he "Prefer Not to Answer" for any question. It is anticipated that this questionnaire will take a participant approximately 20-30 minutes to complete. If the participant completes the Post-Intervention Assessment within the specified time frame then she or he will be eligible to receive an electronic \$5 Amazon gift card (or code).

In addition to the quantitative surveys, participants may be invited to participate in a brief 15-to-30-minute, structured interview about their experiences using the app if they consent to do so on the informed consent document. Participants will be selected for interviews based on the criteria outlined in Section 13.1. If selected for an interview, participants will be contacted via email by a member of the USU team about scheduling the interview two-to-six weeks after being sent the code and instructions to access the app. Interviews will be conducted by a member of the USU team via telephone. Participants who complete the interview off duty will be eligible to receive an additional \$5 Amazon gift card (or code). Non-completion of an interview, for any reason, will not affect a participant's primary participation in the research study.

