The SRH Knowledge Pre-Test Assessment will be administered to participants in the application at the onset of the intervention. The SRH Knowledge Pre-Test will assess baseline SRH knowledge that will be used to tailor select content in the app to the participant (see Study Procedures for more information and examples).

The Participant Post-Test Assessment will be administered to participants after completion of the intervention via an online data collection software (e.g., REDCap, SurveyMonkey). All questions in the Participant Post-Test Assessment must be answered. However, a participant may respond that she or he "Prefer Not to Answer" for any question. The Participant Post-Test Assessment assess sexual and reproductive health (SRH) knowledge, attitudes, self-efficacy, and acceptability of the intervention.

Data will also be collected on participants' interactions with the app. This data includes information such as information on how long participants spent on each component, how many times participants opened the app, and how many times participants accessed and completed components.

Participants who consent to opt-in to an additional structured, qualitative interview will be asked to complete an interview with a member of the USU team via telephone two-to-six weeks after receiving the intervention. The interview will ask participants about their experiences using the app, including-but-not-limited-to questions about graphics (aesthetics), barriers to use, and ease of use (see attached interview agenda). Interviews will be recorded, and recordings will be used to expand notes taken during the interview. Recordings will be deleted upon completion of interview notes.

**10.3 At any point in the study, will you request, use, or access health information in any form, including verbal, hard copy and electronic?**

Yes  No

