**11.0 Statistical/Data Analysis Plan**

**11.1 Statistical Considerations:**

List the statistical methods to be used to address the primary and secondary objectives, specific aims, and/or research hypotheses. Explain how missing data and outliers will be handled in the analysis. The analysis plan should be consistent with the study objectives. Include any subgroup analyses (e.g., gender or age group). Specify statistical methods and variables for each analysis. Describe how confounding variables will be controlled in the data analysis

It is hypothesized that each intervention component will reduce at least some health-risking sexual behaviors (HRSBs) and increase health-promoting behaviors (e.g., condom use, obtaining effective contraception) and that each component will increase at least one antecedent to behavior--knowledge, motivations, or perceptions of behavioral skills. It is expected that each intervention component will have a small-to-medium effect on associated outcomes. Descriptive statistics will be calculated for all data including demographics and outcome variables (e.g., scale scores for attitudes, rates of condom use). Effect coding will be used to indicate the presence or absence of each intervention component. Per the multi-phase optimization strategy (MOST) framework, factorial analysis of variance will be used to calculate both main effects and the theoretically-relevant two-way interaction effects. Secondary analyses will be conducted to examine the information-motivation-behavioral skills (IMB) model whereby behavioral skills serves as a mediator between information and behavior change and between motivation and behavior change. Statistical software such as SAS and R will be utilized for analyses.

Interview data (typed notes) will be analyzed using framework matrix analysis.

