#### **11.6 Data Analysis Plan: Complete description: Background, Objectives, Design, Step by Step how the project is going to be done, Data analysis plan:**

Data analysis will be conducted consistent with the methods described in the "Statistical Considerations" section.

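### Does the plan leave it open whether a component counts as present when it was assigned or when it was used, and does the power statement suffer for it?

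*Combined protocol and SAP*

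**What the plan says.** The statistical text is short. Section 11.1 states that "Effect coding will be used to indicate the presence or absence of each intervention component" and that factorial analysis of variance will estimate main effects and the theoretically relevant two-way interactions. It expects that "each intervention component will have a small-to-medium effect on associated outcomes". Section 11.6 adds nothing further: "Data analysis will be conducted consistent with the methods described in the" statistical considerations section. Neither names an analysis set. The one rule on whose data are analysed is in Section 13.6, which removes the data of participants who ask to withdraw.

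Section 11.5 says that 720 is "sufficient to have 80% power to detect small main effects and interaction effects" at the 5% level. It allows 20% attrition and enrols up to 900. It gives no number for a small effect.

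Non-use is foreseen. Section 13.1 wants interviewees who did and did not use the app, and Section 13.3 identifies them from app analytics. Section 10.2 logs, among other things, "how many times participants accessed and completed components".

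Two phrases look as if they refer to actual use. Section 10.1 explains the on/off level of the narrative videos as "received or not received by a participant". Section 10.2 says: "The Participant Post-Test Assessment will be administered to participants after completion of the intervention". Section 10.1, by contrast, times that assessment "around two weeks after the participant was asked to complete the app".

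**The concern.** In a factorial experiment whose purpose is to choose components, each factor must stay independent of participant characteristics. Assignment guarantees that and receipt does not. Someone who never opens the app receives none of the five components, so coding by receipt makes that person off on all five. The factors become correlated, and any difference between engaged and disengaged people is credited to every component at once. The plan expects such people, logs what would be needed to code this way, and uses the words 'presence' and 'received'.

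The same looseness seems to touch the sample size. If a small effect meant the effect among users, analysis as randomised would dilute it and 720 would give less than 80% power. Finally, an assessment given only after completion would leave non-completers unassessed, so the data would be selected on use. What is at stake is a wrong choice of components, through spurious gains or missed effects.

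**Working it through.** **1. The plan's own figures.** Inputs from Sections 10.1 and 11.5: 2^5 = 32 conditions, 720 evaluable, 80% power, 5% level, 20% attrition. Assumed: two-sided test, SD 1, balanced allocation (360 on and 360 off for each factor).
- Enrolment: 720/(1 − 0.20) = 900, which reproduces exactly.
- Effect detectable with 80% power: (1.960 + 0.842) × √(4/720) = 0.209 SD.
- At exactly 0.20 SD, power at 720 is 76.5% and 786 would be needed. With no number given for a small effect, 720 can be neither confirmed nor refuted. That gap exists whether or not anyone skips the app.

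**2. What coding by receipt would do.** The documents give no rate of non-use, so both inputs are assumptions: a share p never uses the app, and these people score g SD worse. No component has any true effect.
- Correlation between any two component codes: p/(1 + p). At p = 0.20 this is 0.20/1.20 = 0.167. As assigned it is 0.
- False effect per component with five main effects only: 2pg/(1 + 5p).
- p = 0.20, g = 0.5: 0.20/2.00 = 0.10 SD.
- p = 0.10, g = 0.25: 0.05/1.50 = 0.033 SD.

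Simulated false-positive rates at N = 720, averaged over the five components:

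| Coding and model | p = 0.20, g = 0.5 | p = 0.10, g = 0.25 |
|---|---|---|
| By receipt, main effects only | 24% (0.10 SD) | 7% (0.03 SD) |
| By receipt, all two-way interactions | 9% (0.05 SD) | 6% (0.02 SD) |
| By receipt, full 2^5 factorial | 5% to 6% (0.03 SD) | about 5% (0.01 SD) |
| As assigned | about 5% | about 5% |

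The largest figure needs a model without interactions, whereas Section 11.1 plans the relevant two-way terms.

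**3. Does any section point to coding by receipt?**
- Section 9.4 calls the study a randomised factorial experiment, and Section 11.1 names the analysis that goes with that design.
- The gloss "received or not received by a participant" follows directly on the statement that the component is randomised. Later in the same paragraph, people who receive the narrative videos are then expected to watch those assigned. Receiving therefore comes before watching and means being allotted the component. The skills-video paragraph follows the same pattern.
- Section 10.1 also equates the components a participant receives with the treatment condition, and later speaks of the condition as assigned.
- The only use the plan states for app-use data is the choice of interviewees (Sections 13.1 and 13.3).

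**4. Power.** Section 11.5 speaks of main effects and interactions, the quantities that the ANOVA in Section 11.1 estimates. In that analysis a main effect is the on-versus-off contrast over everyone analysed, so non-use is already inside it and power at 0.209 SD is 80% whatever the rate. Only if a small effect meant the effect in users, with none in non-users, would the contrast shrink to 0.209 × (1 − p):
- p = 0.10: 0.188 SD, power 71%.
- p = 0.20: 0.167 SD, power 61%.

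No section mentions an effect in users as a target. People who do not use the app may also be those who skip the survey, in which case they already sit within the 20% attrition.

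**5. Timing of the assessment.** Section 10.1 is the step-by-step procedure, and its trigger is "around two weeks after the participant was asked to complete the app", which reaches non-users. The phrase in Section 10.2 gives the order of events in a list of instruments. The two differ literally, but the procedural text is the one staff would follow.

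**The case for a change.** The strongest reply is that a natural reading is not pre-specification. Non-use is expected, use is logged by component, and the form's prompt in Section 11.1 asks how missing data will be handled, which the answer does not address. An analyst could choose between assignment and receipt after seeing results, and one sentence would prevent it.

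Part of this stands. The analysis set is not written down, a small effect has no number, and the two descriptions of the assessment's timing do not match word for word. A sentence confirming analysis by assigned condition would do no harm.

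It would not, however, alter the analysis that the plan leads to. The harm needs an analyst to depart from the randomised factors without any text telling them to. Rewording Section 10.2 to match 10.1 would also gain little. Under 10.1 the app codes are issued only after the pre-intervention assessment, so someone randomised who never finishes that assessment would still not be reached by the two-week request. Such losses are attrition, for which Section 11.5 allows 20%.

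**Conclusion.** No change is needed. The plan omits a policy that an analyst of a randomised factorial experiment would supply correctly: code and analyse by assigned condition. On that reading the false-positive rate stays at about 5% for any rate of non-use, and non-use shows no power shortfall at 720. The alarming figures (a 24% false-positive rate, or power of 61%) each need a reading that no section supports, together with rates of non-use that the documents do not give. The 24% also needs the planned interactions to be left out. The mismatch between Sections 10.1 and 10.2 is loose wording.

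The conclusion rests on Section 10.1's use of 'receive' for allotment and on main effects in 11.5 meaning the contrasts estimated in 11.1. It would change if the sponsor intended to code by receipt, or had sized the study for an effect in users only. The missing number for a small effect is a separate matter and does not depend on app use.

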#### **11.6 Data Analysis Plan: Complete description: Background, Objectives, Design, Step by Step how the project is going to be done, Data analysis plan:**

Data analysis will be conducted consistent with the methods described in the "Statistical Considerations" section.

### **12.0 Participant Information**

#### **12.1 Subject Population:**

Active duty service members

#### **12.2 Age Range:**

Check all the boxes that apply. If the age range of potential subjects (specimens, records) does not match the range(s) selected, please specify in the text box.

- 0-17
- 18-24
- 25-34
- 35-44
- 45-54
- 55-64
- 65-74
- 75+

17-75+ will be eligible as that is the age range for service members

#### **12.3 Gender:**

- Male
- Female
- Other

#### **12.4 Special categories, check all that apply**

- Minors /Children
- Students
- Employees - Civilian
- Employees - Contractor
- Resident/trainee
- Cadets /Midshipmen
- Active Duty Military Personnel
- Wounded Warriors
- Economically Disadvantaged Persons

- Educationally Disadvantaged Persons
- Physically Challenged (Physical challenges include visual and/or auditory impairment)
- Persons with Impaired Decisional Capacity
- Prisoners
- Pregnant Women, Fetuses, and Neonates
- Non-English Speakers
- International Research involving Foreign Nationals - Headquarters Review is necessary

You must also consider the requirements of DoDI 3216.02, Enclosure 3, paragraph 7.e.

## 12.5 Inclusion Criteria:

Order Number	Criteria
1	Participants are eligible if they are: 1) age 17 or older, 2) active duty military personnel, and 3) willing to be participate in all study activities if eligible and enrolled.

## 12.6 Exclusion Criteria:

Order Number	Criteria
1	Any participant (i.e., service member or provider) will be deemed ineligible to participate if they do not meet the eligibility criteria or are 1) unable to read, speak, or comprehend English, or 2) unable or unwilling to give informed consent.

## 13.0 Recruitment and Consent

### 13.1 Please describe the recruitment process, including how subjects will be identified and selected for the study.

Participants will be recruited across services via advertisement (e.g., physical posters, social media, condoms, nominal items like stress balls), word of mouth, or by approaching or being approached by a research team member, as well as via email or listserv. Individuals who express interest in taking part in the study will be asked to provide consent to be screened for eligibility (Eligibility Screening Questionnaire attached). After completing the screening, eligible individuals will be asked to provide informed consent, which will be collected by USU-based research team members.

The study sample will represent a convenience sample of individuals who voluntarily express interest in participating. Purposive sampling will also be employed to ensure adequate representation of female and male participants and each branch of the military. Participants will complete the intervention off-duty to minimize impact on military operational effectiveness.

Purposive sampling will also be employed when selecting interview participants from the group of participants who consented to complete an interview if selected. Participants will be selected to ensure appropriate representation of gender, sexual, and/or ethnic/racial identity and military rank and/or service and to ensure that there is a good mix of those who have and have not used the app. Demographics information from the Pre-Intervention (baseline) Assessment and analytics data on app use will be used to inform the selections. It will still be expected that participants complete this part of the study off duty as well.

### 13.2 Compensation for Participation:

Participants will be compensated for their participation via electronic Amazon gift cards (codes). Participants will be eligible to receive an electronic \$5 Amazon gift card upon completion of the Participant Post-Intervention Assessment within the specified period of time if they indicate that they completed the survey off duty. Participants who complete the interview will be eligible to receive an additional \$5 Amazon gift card upon completion of the interview off duty.

**13.3 Please describe the pre-screening process. If no pre-screening, enter Not Applicable in the text editor**

Participant eligibility in the overall study will be determined by anonymous self-reported responses to screening questions including age and active duty military status. Participants will be invited to complete an interview based on their answers to demographic questions in the de-identified Pre-Intervention Assessment and whether or not they used the app (pulled from de-identified app analytics data). Medical records from the Military Health System (MHS) will not be utilized at any point during the study, and will not be used to identify subjects or confirm eligibility.

**13.4 Consent Process: Revised Common Rule, Section 219.116: General requirements for informed consent, whether written or oral, are set forth in this paragraph and apply to consent obtained in accordance with the requirements set forth in paragraphs (b) through (d) of this section. Broad consent may be obtained in lieu of informed consent obtained in accordance with paragraphs (b) and (c) of this section only with respect to the storage, maintenance, and secondary research uses of identifiable private information and identifiable biospecimens.**

Are you requesting a waiver or alteration of informed consent?

Yes  No

Please explain the consent process:

After completing the Eligibility Screening Assessment, all eligible and interested individuals will be engaged in an electronic informed consent process via a secure, online collection software (e.g., REDCap, SurveyMonkey) prior to completing any other assessments, the study intervention, or qualitative interview. The informed consent document (ICD; attached) includes an explanation of the nature and purpose of the study, study procedures, risks and benefits, confidentiality, and the voluntary nature of research studies. Prospective participants will be instructed on the consent form to call or email the Uniformed Services University of the Health Sciences (USU) research team with any questions. Once the signed ICD is returned to the study team, the participant will be permitted to be engaged with the intervention, assessments, and all other aspects of the study for which they consent (see Study Procedures). Participants will be informed to check an additional box after the signature line if they consent to be contacted about and participate in the qualitative interview. Participants will be offered a copy of their signed ICD.

**13.5 DoDI 3216.02 requires an ombudsman to be present during recruitment briefings when research involves greater than minimal risk and recruitment of Service members occurs in a group setting. If applicable, you may nominate an individual to serve as the ombudsman.**

N/A  
 Propose ombudsman

